Official Title

The Learning Outcome of Resuscitation Teamwork Training on
Developing Teamwork Performance in Postgraduate Year
Doctors and Nurses - Comparison of Board Game-based
Learning, Simulation-based Learning and lecture-based learning

- **ClinicalTrials.gov ID:** NCT05302414
- **Protocol ID:** N201912063 (Taipei Medical University-Joint Institutional Review Board)
- **Document date:**
 - **Application Form:** Version 3.0 / 20220623
 - **Other Appendix:** Version 2.0 / 20220623
 - **Informed Consent Forms:** Version 2.0 / 20220211
 - **Protocol Version/ Date:** Version 2.0 / 20220211
 - **Case Report Forms:** Version 1.0 / 20220110

Objectives:

The aim of this study was to compare the effectiveness of board game-based learning, simulation-based learning, and interactive lecture-based learning in enhancing resuscitation medical knowledge, teamwork knowledge, medical task performance, and teamwork performance among postgraduate-year residents and nurses undergoing resuscitation teamwork training.

Methods:

Utilizing a single-blind, prospective, randomized controlled trial approach, this study enlisted 96 postgraduate-year nurses and physicians through convenience sampling. The participants were divided into three groups: the Board Game-Based Learning Group (Experimental Group I), the Simulation-Based Learning Group (Experimental Group II), and the Interactive Lecture-Based Learning Group (Control Group), with each group comprising 32 individuals. Evaluations of effectiveness were conducted at three points: pretest, posttest, and at a three-month follow-up. The instruments for measurement included assessments of team performance observation tool, knowledge of teamwork assessment, interprofessional collaboration scale, resuscitation knowledge scale, medical task performance, learning cognitive load, and course survey. Two evaluators, unaware of which teaching method the team received, independently used standardized assessment forms to evaluate the medical team's resuscitation actions and teamwork behavior in scenario-based simulations through video observation, ensuring objectivity and reliability.

Statistical:

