In this study, the presentation of categorical variables was conducted using frequencies and percentages, while continuous variables were summarized through means and standard deviations. The chi-squared test was applied to examine the demographic characteristics at the outset. Given the data's deviation from a normal distribution, a non-parametric approach was adopted for analysis, with the median and interquartile range (IQR) providing insights into the data's central tendency and dispersion. This method, unaffected by outliers, offers a more accurate depiction of data that does not follow a normal distribution. To identify differences across the three groups, the study utilized the Kruskal-Wallis H-test. The Friedman test was used to evaluate changes within groups, whereas the Wilcoxon test facilitated pairwise comparisons at various assessment points. GEE analysis was employed to compare the effectiveness of the intervention across different time points among the three groups. Text mining techniques were used to analyze feedback from course collections. IBM SPSS version 20 was the tool for all data analyses. The criteria for statistical significance were established using a two-tailed test, setting the P-value threshold at < 0.05 .

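### The three within-arm Wilcoxon time-point comparisons are neither tied to the Friedman test nor adjusted, so an arm with no change shows at least one significant pair about 12-13% of the time (minor)

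*Combined protocol and SAP*

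**What the plan says.** The Methods section fixes the number of looks: "Evaluations of effectiveness were conducted at three points: pretest, posttest, and at a three-month follow-up". It gives the arm size as well: "with each group comprising 32 individuals".

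The Statistical section assigns two procedures to change over time inside an arm. For the overall question, "The Friedman test was used to evaluate changes within groups". For the specific pairs of time points, "the Wilcoxon test facilitated pairwise comparisons at various assessment points". The only decision rule covers all analyses: "The criteria for statistical significance were established using a two-tailed test", "setting the P-value threshold at < 0.05".

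The section does not say whether the Wilcoxon pairs depend on the Friedman result, whether they have an order, or whether they are adjusted. It does not say whether Wilcoxon means the signed-rank or the rank-sum test. Kruskal-Wallis and GEE are assigned separately to differences among the three groups.

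**The concern.** The three pairs are pretest-posttest, pretest-month 3 and posttest-month 3. They locate change within an arm: whether scores rose after training, and whether the gain held or decayed. With three arms there are 3 × 3 = 9 such tests for every outcome measured at all three points.

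If each pair is read on its own at 0.05, the three share no 5% limit, and a pair can be declared significant in an arm whose Friedman test is not. The plan leaves open which reading applies, so that choice could be made once the results are known. Controlling the between-arm tests would not close this gap, because it is a separate family of tests.

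**Working it through.** **Inputs from the documents.** Two-sided threshold 0.05 (Statistical); three time points and 32 people per arm, 3 × 32 = 96 in total (Methods).

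**Inputs assumed.** Wilcoxon is the signed-rank test. People are independent with complete data. The correlation between time points is not given, so a range was used: equal correlation 0 to 0.8, and serially decaying correlation 0.5 and 0.8. Scores were normal, tied or heavy-tailed.

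**Step 1: the plan's own figure.** One signed-rank test at n = 32 with no true change rejects in 4.9-5.1% of simulated trials. The stated 0.05 is reproduced for a single test.

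**Step 2: three pairs, no change at any time point.**
- If the three tests were independent: 1 − 0.95³ = 0.143. This is too high, because the pairs share data.
- For three exchangeable normal means, at least one pair exceeds 1.96 when the studentized range exceeds 1.96 × √2. That probability is 0.122.
- Direct simulation of the three signed-rank tests at n = 32 (100,000 replicates per setting):

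| Setting | At least one pair P < 0.05 | Same, only if Friedman P < 0.05 |
|---|---|---|
| Equal correlation 0 | 12.4% | 4.1% |
| Equal correlation 0.5 | 12.6% | 4.1% |
| Equal correlation 0.8 | 12.5% | 4.1% |
| Serial correlation 0.5 | 12.1% | 4.0% |
| Serial correlation 0.8 | 11.9% | 4.1% |
| Correlation 0.5, tied scores | 12.2% | 4.3% |
| Correlation 0.5, heavy tails | 12.5% | 3.9% |

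In about 8% of no-change arms a pair is significant while Friedman is not (12.6% − 4.1% = 8.5% at correlation 0.5). Whether Friedman is a gate therefore decides most of the false findings.

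**Step 3: which false statements.** The 12-13% counts either direction on any pair. With no change and correlation 0.3-0.7:
- false improvement from pretest (to posttest or month 3): about 4.5-4.8%;
- false decline from posttest to month 3: about 2.4-2.6%;
- either of these: just under 7%.

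**Step 4: real and retained learning.** With a 1 SD gain that holds, both comparisons with pretest are true effects. Posttest versus month 3 is the one true null, and it rejects in 5.0% of trials. Over three such arms the chance of at least one is 1 − 0.95³ = 0.143. Friedman is significant in 99.9% of these trials, so gating on it leaves the figure essentially unchanged.

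**Step 5: why the gate controls the rate.** If all three time points are equal, any claim must first pass Friedman at 5%. If they are not all equal, at most one pair can be a true null, and that pair is tested at 5%. With three time points the limit therefore holds under every pattern.

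**Step 6: power cost of the gate** (retained gain, normal scores, correlation 0.5, pretest-posttest):

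| Gain | As written | Friedman gate |
|---|---|---|
| 0.5 SD | 0.76 | 0.61 |
| 0.8 SD | 0.99 | 0.97 |

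**The case against.** The strongest reply is that the plan already implies a gate. One sentence pairs an omnibus test with a pairwise test, which is how post hoc testing is usually described, and nothing forbids making Wilcoxon conditional on Friedman. If that was the intention, the rate is already about 4%. This stands in part: the text is silent and is not a decision against gating. But the two tests are set side by side with no condition, and a reader cannot tell which rule was applied.

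The second reply is that the objective is a comparison among three teaching methods, served by Kruskal-Wallis and GEE. That stands in full. The within-arm pairs carry no randomised contrast, so the point is minor.

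Three stronger readings are tempting, and the documents do not support them.
- A reader might infer that false claims of learning or decay occur more than twice as often as 5%. They do not. The 12-13% also counts falls from pretest and rises after posttest; for improvement from pretest or decline by month 3 the figure is about 7%.
- A reader might infer that 12-13% applies to the trial as it will probably run. It requires no change at all three points in an arm. Combining arms, 1 − (1 − 0.122)³ = 32%, requires that in all three trained arms.
- A reader might infer that these pairs are the only within-arm tests. Friedman is also assigned to change within groups; only the location of that change rests on Wilcoxon.

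**Conclusion.** The gap is real and minor. As written, three Wilcoxon pairs per arm and outcome are each judged at 0.05 with no gate, order or adjustment. With no change at any time point, at least one is significant about 12-13% of the time in either direction. With real, retained learning the exposure is 5% per arm, on posttest versus month 3 only.

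These rates rest on the signed-rank reading and on 32 independent complete cases per arm. The Methods section describes evaluators rating the medical team's behaviour, and the number of teams is not given. If the team is the unit of analysis, the ungated rate is about 12.7% with an assumed 16 units and 14% with 8, so the point does not shrink. If team members share one score and are analysed as individuals, even a single test no longer holds 5%, and a gate does not repair that.

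Nothing here bears on the randomised between-arm comparison.

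**What to change.** Replace the Wilcoxon wording in the Statistical section with: *Within each arm and outcome, pairwise Wilcoxon signed-rank tests are interpreted only when the Friedman test has P < 0.05; otherwise they are reported as descriptive.* For outcomes scored per team, add that the team is the unit in both tests.

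This keeps both planned tests and needs no new data. The cost is the loss of power for moderate gains shown in the working; at 0.8 SD it is small.

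Testing pretest-posttest first also holds 5% and keeps that pair's power at 0.76 for a 0.5 SD gain. However, it makes the planned Friedman test descriptive. For a change that appears only at month 3, it cuts pretest-month 3 power from about 0.76 to 0.03 at 0.5 SD. The gate is the smaller departure from the plan.

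The section is in the past tense and refers to the observed distribution of the data. If the results had already been examined when the rule was added, the report should say so.

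### The GEE comparison states no variance estimator, reference distribution or cluster unit; under the usual uncorrected sandwich Wald test the joint group-by-time test exceeds its 5% level, modestly at 32 persons per arm and heavily if teams are the units

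*Combined protocol and SAP*

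**What the plan says.** The Statistical section gives GEE one sentence: "GEE analysis was employed to compare the effectiveness of the intervention across different time points among the three groups". The significance rule applies to all tests: "The criteria for statistical significance were established using a two-tailed test", "setting the P-value threshold at < 0.05". Nothing is said about the variance estimator, the reference distribution, the working correlation, the cluster unit or a small-sample correction.

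The Methods section supplies the design. There are 96 participants in three arms, "with each group comprising 32 individuals". On timing: "Evaluations of effectiveness were conducted at three points: pretest, posttest, and at a three-month follow-up". Two blinded evaluators used standard forms "to evaluate the medical team's resuscitation actions and teamwork behavior in scenario-based simulations through video observation", so these ratings describe a team. Neither the team size nor the number of teams is given.

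The Statistical section also says: "Given the data's deviation from a normal distribution, a non-parametric approach was adopted for analysis". It lists Kruskal-Wallis for differences between arms, and Friedman and Wilcoxon tests for changes within arms.

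**The concern.** Among the listed methods, only GEE compares the three arms and the three time points together. The usual GEE inference pairs a sandwich variance with a chi-square or normal reference, and both are large-sample results. With few independent units the sandwich is biased downward, and the reference distribution ignores the fact that the variance is itself estimated. Both errors lower the P-value, and they matter more as the test has more degrees of freedom and the clusters become fewer.

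At stake is whether the declared 0.05 is the level at which the trial actually tests, and whether intervals have their nominal coverage. The problem is most acute for the team-scored outcomes, where the number of independent units per arm must be below 32.

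**Working it through.** **Inputs from the documents.** Three arms, n = 32 persons per arm, three time points, two-tailed α = 0.05. Group-by-time df = (3−1)(3−1) = 4.

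**Assumptions, not in the documents.** Uncorrected sandwich variance; Wald chi-square (or z) reference; complete, balanced data; a saturated group × time mean model. Teams are formed within arms and stay the same over time. Teams of 2, 4 or 8 give 32/2 = 16, 32/4 = 8 or 32/8 = 4 teams per arm.

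The plan has no test-size or power calculation to reproduce. Its only relevant figure is the nominal 0.05.

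**Statistic.** For each unit take the two changes from pretest. Let m_g be the mean change vector in arm g, and S_g the sum over units of e e′ divided by n², where e is the residual from m_g. With θ = (m₁−m₃, m₂−m₃), V has diagonal blocks S₁+S₃ and S₂+S₃ and off-diagonal block S₃. Then W = θ′V⁻¹θ is referred to chi-square on 4 df (critical value 9.49). On a test dataset this closed form and a standard GEE routine with exchangeable correlation both gave 4.0732. With balanced complete data the working correlation does not alter W.

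**Single contrast, checked by hand.** For normal scores the sandwich variance is (n−1)/n times the unbiased one, so rejecting at |z| > 1.96 is the same as rejecting at |t| > 1.96·√((n−1)/n) on 2(n−1) df.

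- n = 32: 1.96·√(31/32) = 1.929 on 62 df, true level 5.8%. The standard error is too small by 1 − √(31/32) = 1.6%.
- n = 8: 1.96·√(7/8) = 1.833 on 14 df, true level 8.8%.

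Simulation agrees: 5.8–5.9% (normal) and 5.4–5.6% (lognormal) at n = 32, and 8.9% (normal) at n = 8.

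**Joint 4-df test, simulated under the null** (40,000 trials per scenario, Monte Carlo standard error about 0.1 percentage points):

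| Independent units per arm | Normal scores | Lognormal scores |
|---|---|---|
| 32 (persons; correlation 0.2–0.8) | 7.4–7.7% | 6.4–7.1% |
| 16 (correlation 0.5) | 11.1% | 9.4% |
| 8 (correlation 0.5) | 19.4% | 17.0% |
| 4 (correlation 0.5) | 42.5% | 40.1% |

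Ceiling-limited scores at 32 per arm also give 7.4–7.7%. With 28 or 26 persons per arm (normal) the level is 8.0% or 8.4%.

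**Other choices that the wording allows.**

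- Model-based exchangeable variance, correctly specified, with chi-square: 5.3% at 32 per arm, 5.8% at 16, 6.7% at 8, 9.2% at 4.
- Persons as clusters when each member carries the team's score: about 78% (teams of 4) and 96% (teams of 8).

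**Candidate corrections.** In this design a Kauermann-Carroll-type correction multiplies V by n/(n−1), and a Mancl-DeRouen-type correction by (n/(n−1))². Put ν = 3(n−1), so ν = 93 at n = 32 and 21 at n = 8.

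- Single contrast, Kauermann-Carroll-type with t on 2(n−1) df: about 5% at 32 and at 8 per arm (normal); 3.9–4.4% at 8 (lognormal).
- Joint test at 8 per arm, normal scores, W/4 referred to F(4, ν−3) without scaling: about 6.6% (Mancl-DeRouen) or 9.2% (Kauermann-Carroll).
- Joint test, Mancl-DeRouen, W(ν−3)/(4ν) referred to F(4, ν−3): 4.6–4.8% at 32, about 4% at 8 and 3.9% at 4 (normal); about 3% at 8 (lognormal).
- Joint test, pooled unstructured-covariance model with an F reference: 4.6–4.9%.

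**The case against.** The strongest reply is that the inflation belongs to an analysis the plan does not specify. No variance estimator is named, and a correctly specified model-based variance holds 5.3% at 32 per arm. No joint 4-df test is named either; if inference rests on single coefficients, the level at 32 per arm is at most about 6% and the standard error is off by 1.6%. The team figures depend on an assumed team size. Treating persons as clusters for team scores is a unit-of-analysis problem that no sandwich correction repairs.

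Most of this stands, and it limits the point. A reader might infer that the plan is wrong as written and its intervals are demonstrably too narrow; the text is silent on the choices that decide this. A reader might also infer that GEE carries the trial's answer for every instrument. No primary analysis is named, Kruskal-Wallis also compares arms, and the instruments analysed by GEE are not listed. Nor is it supported that the error is more than half as large again as stated. At 32 per arm it is about half with normal scores and less with skewed ones, and the plan itself reports non-normal data.

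What does not stand is the idea that silence makes the matter harmless. The usual sandwich Wald test misses the level. The model-based alternative depends on a working correlation that is not stated, and it too drifts upward with few teams.

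**Conclusion.** The concern holds conditionally. With an uncorrected sandwich and a Wald chi-square, complete data and three time points, the joint group-by-time test at 32 independent persons per arm has a true level of about 7.4–7.7% (normal) or 6.4–7.1% (skewed) against a declared 5%. Single contrasts, at about 5.4–6%, are close to nominal.

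For team-scored outcomes the joint test's error is about 9–11%, 17–19% or 40–43% with 16, 8 or 4 teams per arm. This is a range over assumed team sizes, and none of these figures can be read as this trial's own error rate. For person-level outcomes the correction is a modest, cheap improvement. For team-scored outcomes it could change conclusions.

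**What to change.** State in the Statistical section, for each outcome, the cluster unit, the variance estimator and the reference distribution; report the number of teams per arm. Then:

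- **Single arm contrasts:** Kauermann-Carroll-type variance with t-based intervals on about 2(n−1) df.
- **Joint group-by-time test:** either a linear mixed model with unstructured covariance over time and Kenward-Roger or Satterthwaite df, or a Mancl-DeRouen variance with W(ν−3)/(4ν) referred to F(4, ν−3), ν = 3(n−1). At 32 per arm that is F(4, 90). Write the scaling factor out, because an unscaled F does not restore the level with few teams.
- **Team-scored outcomes:** one record per team per time point, with n the number of teams. A small-sample correction with persons as clusters does not fix shared team scores.

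The cost is a few lines of SAP text and a rerun on existing data, possibly outside the named software. Intervals become slightly wider, and the tests are somewhat conservative with skewed scores. The mixed-model figure above comes from a pooled-covariance stand-in, so its level should be confirmed at the actual number of teams.
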